2.4. Additional Parameters

In addition to the protocol-specified efficacy endpoints, other meaningful parameters may be analyzed, such as combined PUL dimensions (e.g., combined mid-level (elbow) and distal-level (hand and wrist) dimension) for the ITT Population and PP Populations.

2.5. Data Visualization

Figures depicting model-adjusted least-squares means (LS-Means) by visit broken out by treatment arm will be produced for the primary, secondary, and some exploratory efficacy outcomes. This will apply to both raw and transformed outcome measures and their corresponding model estimates.

A forest plot will be produced for all PUL endpoints showing the magnitude, significance, and errors associated with several measures at Month 12 simultaneously. This plot will also include the GST of all PUL outcomes at Month 12. The same forest plot will be produced for Cardiac MRI outcomes, including the corresponding GST. Forest plots will only be produced for transformed outcome measures.

All figures will be produced for the ITT Population only.

2.6. Protocol-Specified Endpoints Previously Removed from Analysis

The final version 3.0 of the statistical analysis plan removed some protocol-specified exploratory endpoints from the final analysis. This Addendum reinstates the following exploratory efficacy endpoints for analysis:

- High-level (shoulder) dimension of the PUL 1.2;
- Distal-level (wrist and hand) dimension of the PUL 1.2;
- High-level (shoulder) dimension of the PUL 2.0;
- Distal-level (wrist and hand) dimension of the PUL 2.0;
- Grip strength, percent predicted, at Months 3, 6, 9, and 12;
- Tip-to-tip pinch strength, percent predicted, at Months 3, 6, 9, and 12;
- Key pinch strength, percent predicted, at Months 3, 6, 9, and 12;
- Elbow flexion strength, percent predicted, at Months 3, 6, 9, and 12;
- Pediatric Outcomes Data Collection Instrument (PODCI) scales (subject and parent) at Months 3, 6, 9, and 12;
- Parent/caretaker-reported DMD Lifetime Mobility Scale (DMD-LMS) at Months 3, 6, 9, and 12;

- North Star Ambulatory Assessment (NSAA) at Months 3, 6, 9, and 12;
- Biomarkers at Months 3, 6, 9, and 12.

All PUL and strength endpoints above will be analyzed using summary statistics, the primary MMRM, and the percentile ranked model described above for the ITT and PP Populations. All available data listed for the ITT population.

CK Isoenzyme biomarkers will be analyzed similarly but for the safety population, with all available data listed for the safety population within the serum chemistry laboratory listing.

Other biomarkers will be analyzed only using the percentile ranked model for the ITT population, with all available data listed for the ITT population.

PODCI, parent/caretaker-reported DMD-LMS, and NSAA endpoints above will be listed for the ITT Population.

The following exploratory efficacy endpoints will not be reinstated:

- 10-Meter Walk/Run Time (10MWRT) at Months 3, 6, 9, and 12;
- Incidence of loss of ambulation (10MWRT > 30 seconds) at Months 3, 6, 9, and 12;
- Resource utilization, including hospitalizations for orthopedic injury or surgery and for pulmonary infections, over the course of the trial.

3. Safety Analyses

3.1. Adverse Events

This study utilized an independent Clinical Events Committee (CEC) to adjudicate all potential primary safety endpoints. The CEC data review was conducted in a blinded fashion and the results were provided only when the adjudication process yielded a different conclusion on the Treatment-Emergent Adverse Events (TEAE) as compared to the original TEAE assessment (i.e., the raw TEAE data). Since the adjudicated AE data set only contains the subset of adverse events which the adjudication committee reviewed, these data will be listed separately and not summarized due to their sparseness. In order to provide a comprehensive assessment of all TEAEs, the raw TEAE data will be reported in listings and summary tables for the safety population.

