7.1 Adverse Events

AEs will be coded using MedDRA coding system (Version 21.0). Potential primary safety endpoints, described in Section 2.2.1, will be adjudicated by an independent Clinical Events Committee (CEC).

The following AEs are defined as treatment-emergent AEs (TEAEs):

- AEs occurring after the initiation of the IV catheter placement for the initial dose of IP; or
- AEs with completely missing start date, or similarly, AEs that started the same month and year as IP administration but with missing start day.

Subject listings of all adverse events as reported will be provided. A separate listing will be done for TEAEs as adjudicated by the CEC. Serious AEs, primary safety endpoints as adjudicated, TEAEs adjudicated as related to IP or administration procedure, and hypersensitivity reactions as adjudicated will be listed separately.

All summary tables will be reported using TEAEs as adjudicated by the CEC. A summary of the primary safety endpoints will be presented. In addition, TEAEs related to IP or administration procedure and hypersensitivity reactions will be summarized.

AEs will be displayed by MedDRA SOC and PT, with subjects who have the same AE counted only once for that event and subjects who have more than one AE within a SOC counted only once in that SOC. The numbers and percentages of subjects reporting an event, as well as the number of events that were reported, will be calculated by treatment group.

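### SAP 7.1 and SAP Addendum 3.1 conflict on whether the primary safety endpoint summary uses CEC-adjudicated or raw adverse events

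*SAP*

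**What the plan says.** **Protocol.** The Synopsis and section 15.2 set up a blinded CEC whose task is to adjudicate every potential primary safety endpoint event. Section 14.4.1 names the primary safety endpoints as incidences through Month 12 and has the arms summarized and compared on them. Section 14.4.2, on general adverse event reporting, lists and summarizes reported events without mentioning adjudication. Section 14.4 states that safety carries no formal hypothesis test.

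**SAP v3.0.** Section 7.1 says: "All summary tables will be reported using TEAEs as adjudicated by the CEC". It continues: "A summary of the primary safety endpoints will be presented", and adds that "TEAEs related to IP or administration procedure and hypersensitivity reactions will be summarized". It also plans separate listings of adjudicated events. Section 7.1.1 lets the CEC merge reported events, rename them, or decide that a report is not an adverse event.

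**SAP Addendum.** Section 3.1 explains that "the results were provided only when the adjudication process yielded a different conclusion", and that "the adjudicated AE data set only contains the subset of adverse events which the adjudication committee reviewed". It concludes that "these data will be listed separately and not summarized due to their sparseness". It gives full coverage as its aim ("In order to provide a comprehensive assessment of all TEAEs") and, for the displays themselves, decides that "the raw TEAE data will be reported in listings and summary tables for the safety population".

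**The concern.** The two sections give different data sources for the same displays. SAP 7.1 takes all summary tables from adjudicated events. Addendum 3.1 keeps only a listing of adjudicated data and takes the tables from raw events. The Addendum's introduction says only that it gives more detail on adverse event summaries, yet section 3.1 reverses their source. For efficacy, Addendum 2.6 names which SAP v3.0 decisions it undoes. For safety there is no such statement.

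The display at stake is the primary safety endpoint table. Safety here is descriptive, so that table is the primary safety result. With only a listing, a reader would have to rebuild adjudicated incidence by arm by hand, and the result might not match the raw tables printed beside it.

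Two of the endpoints are also not single coded terms. SAP 2.2.1 defines hypersensitivity reaction by onset, duration and absence of infection. It defines immune sensitization syndrome by clinical signs together with donor-specific antibody thresholds. Raw tables by system organ class and preferred term do not apply those definitions by themselves.

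**Working it through.** The documents give no figure to reproduce. The check is a comparison of texts, followed by a calculation of scale.

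**1. The two instructions side by side**

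| Item | SAP 7.1 | Addendum 3.1 |
|---|---|---|
| Source of summary tables | Adjudicated events | Raw events |
| Adjudicated data | Listed and summarized | Listed only |
| Primary safety endpoint summary | Promised | Not mentioned, not exempted |
| Related events and hypersensitivity summaries | Promised | Not mentioned, not exempted |
| Relation to the other text | Earlier | Later; does not say that it replaces 7.1 |

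Both instructions cannot be followed for the endpoint table.

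**2. Does the stated reason reach the endpoint table?** Addendum 3.1 gives two reasons: the CEC file is a sparse subset, and all treatment-emergent events should be covered. Both support not tabulating the CEC file alone, and both support raw tables for general reporting. Neither blocks an adjudicated endpoint table, whichever way the CEC file is read:

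- If the file holds only events on which the CEC differed, every other event keeps its original assessment. Raw records with the CEC changes applied then form a complete adjudicated set.
- If the file holds all reviewed events, it should contain the potential primary safety endpoint events, because reviewing those is the CEC's task (Protocol 15.2, SAP 7.1.1).

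The documents do not say whether the file carries endpoint flags or links to the raw records. That has to be confirmed.

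**3. Scale**

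Inputs: 20 randomized at 1:1 (SAP 3.1). The interim analysis paragraph of the Protocol Synopsis refers to twenty treated subjects, so the safety population is taken as 20. Arm sizes are not stated; 10 per arm is assumed, with 8 to 12 as a range.

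Shift in one arm's incidence when one subject's only qualifying event is reclassified = 1/n:

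- n = 10: 1/10 = 10.0 percentage points
- n = 12: 1/12 = 8.3 points
- n = 8: 1/8 = 12.5 points

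Effect on the between-arm difference if one such subject is removed from each arm:

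- 10 and 10: 10.0 − 10.0 = 0
- 8 and 12: 12.5 − 8.3 = 4.2 points

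Merging two reports of one event in one subject changes the event count but not subject incidence.

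**The case against.** The strongest reply is that SAP 7.1 may still stand. SAP section 8 says expressly that v3.0 supersedes earlier versions, whereas the Addendum makes no such claim and calls its analyses post hoc. On that view the adjudicated endpoint summary is still planned. This much stands: a reader might infer that no adjudicated table of the primary safety endpoints will exist, or that the table will be built from raw data, and the documents do not establish either. Addendum 3.1 does not name that table, and SAP Appendix F, which lists the final tables, is blacked out and cannot settle it. What remains is that the later text says the adjudicated data will not be summarized and makes no exception, so the conflict is real.

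Second, raw tables agree with the protocol for general reporting. Protocol 14.4.2 applies no adjudication filter, and Protocol 13.2.2 makes relatedness the investigator's judgement. The CEC reviews only potential primary safety endpoints, so its file alone could not support every table in SAP 7.1. This stands, and it narrows the point to the endpoint displays, among which SAP 7.1 includes related events and hypersensitivity reactions.

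Third, a reader might take the two descriptions of the CEC file as a contradiction. They can be read together: discordant results necessarily come from reviewed events. The wording is loose and needs clarifying, no more.

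Fourth, the change is open, reasons are given, and the adjudicated data are still listed. Protocol 14.1 asks for deviations from the SAP to be explained in the study report, which is not among the documents, so no breach of it can be shown. That also stands. What is missing is a cross-reference to SAP 7.1 and a reason that applies to the endpoint table.

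**Conclusion.** The point holds as an unreconciled conflict between SAP 7.1 and Addendum 3.1 over the data source for the primary safety endpoint summary. The loss of an adjudicated incidence table by arm is conditional: it follows if the Addendum governs. The Addendum's reasons support raw tables for general adverse event reporting, but not removing adjudication from the endpoints that the CEC exists to classify.

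The size of any effect on the reported results is unknown. The number and direction of CEC changes are not given and may be zero. On the assumption of 10 subjects per arm, each subject whose only qualifying event is reclassified moves that arm's incidence by 10 points (8.3 to 12.5 points for arms of 12 to 8). That is a statement of sensitivity in a small trial, not evidence that raw and adjudicated incidence differ. No formal test is affected. The point is worth fixing because the display is a primary result and the remedy is cheap.

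**What to change.** - State in the Addendum which section governs the primary safety endpoint table.
- State whether the CEC file holds all reviewed events or only those on which the CEC differed from the original assessment.
- Add a by-arm incidence table of the primary safety endpoints as adjudicated, including related treatment-emergent events and hypersensitivity reactions. Build it by overlaying CEC conclusions on the raw adverse event records, and list each CEC change beside its original record.
- Keep the raw tables as the comprehensive display.
- If the records cannot be linked or endpoint classifications are not available, say so, and describe and justify the departure from SAP 7.1 in the study report, as Protocol 14.1 provides.

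The cost is a record-linkage step, possibly a query to the CEC for endpoint classifications, and a few extra tables. No new subject data are needed.

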3.2. Cardiac and Steroid Medications

Frequencies and percentages of subjects reported or receiving WHODrug Global cardiac medications at any time on or after Day 1 (date of first IP exposure) will be both summarized by WHODrug Global Anatomic Therapeutic Chemical (ATC) Level 2 and Preferred Term and listed.

Frequencies and percentages of subjects reported or receiving WHODrug Global steroid medications at any time on or after Day 1 (date of first IP exposure) will be summarized separately for systemic use and non-systemic use, where steroid medications with reported

indications as DMD, DMD treatment, or SOC for DMD are considered for systemic use, and steroid medications with other indications are considered for non-systemic use. Both summaries will be presented by WHODrug Preferred Term. All steroid medications on study, along with their reported indications, will be listed.

4. Pharmacoeconomic Analysis

An exploratory analysis was planned to explore all-cause hospitalizations, hospitalizations for orthopedic injury/surgery or pulmonary infections, and antibiotic usage. Billing information was not to be collected; rather, standardized, composite or bundled costings of national averages was planned to be used in the analysis. Given the small sample size and minimal observations on trial, this analysis was not completed.

References

1. Siegel S. Nonparametric Statistics. Am Stat 1957;11(3):13–9.
2. Mallinckrodt CH. and Ilya Lipkovich. A practical guide to analyzing longitudinal clinical trial data. CRC Press. Boca Raton. 2017 (Chapter 11).
3. O'Brien PC. Procedures for comparing samples with multiple endpoints. Biometrics 1984; 40: 1079-87.

Signature Approval of SAP Addendum – Post Hoc Analysis HOPE-2 Study

A Phase 2, Randomized, Double-Blind, Placebo-Controlled Trial Evaluating the Safety and Efficacy of Intravenous Delivery of Allogeneic Cardiosphere-Derived Cells in Subjects with Duchenne Muscular Dystrophy (HOPE-2)

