10.7. Administration

All investigational product (IP; CAP-1002 or placebo) delivery will be conducted in an outpatient setting at the investigative site on Day 1 and Months 3, 6, and 9. Subjects must complete all other trial assessments prior to IP infusion, excluding those related to the IP infusion (e.g., post-infusion

monitoring).

Prior to each infusion, it is recommended that site personnel meet to discuss the logistics for that specific infusion.

Capricor requires that subjects be treated prior to each IP infusion with medications to minimize the risk of potential severe allergic reaction. It is strongly encouraged that pre-medication be administered according to the guidelines in Section 21.2, however, investigative sites may use institutional protocols established for anaphylaxis prevention should they be at least physiologically comparable to the guidelines in Section 21.2.

[REDACTED]

[REDACTED]

[REDACTED]

[REDACTED]

[REDACTED]

[REDACTED]

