12.4. Prior and Concomitant Medications

All medications taken within one month prior to the screening visit through trial completion will be captured. Medications will be reviewed at each trial visit and any medication changes, including new and discontinuations, will be recorded.

For each medication, generic name, indication, dose, frequency, route, and starting and stopping dates/times (if applicable) will be collected. The trade name of the medication is to be reported for combination therapies (e.g., Alka-Seltzer, Advair, etc.).

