21. APPENDICES

21.1. Appendix I: Exon 44-Skip Amenable Dystrophin Mutations

Deletions to the following exons of the dystrophin gene are amenable to exon-44 skipping ([den Dunnen J.T., 2014](#); [White and den Dunnen, 2006](#); [Aartsma-Rus et al., 2006](#); [Aartsma-Rus, 2014](#)):

10-43	24-43	34-43	45
11-43	25-43	35-43	45-54
13-43	26-43	36-43	45-56
14-43	27-43	37-43	45-62
15-43	28-43	38-43	
16-43	29-43	39-43	
17-43	30-43	40-43	
19-43	31-43	41-43	
21-43	32-43	42-43	
23-43	33-43	43	

21.2. Appendix II: Pre-Infusion Guidance for Minimizing Risk of Potential Severe Hypersensitivity Reaction

As discussed in Section 10.6, Capricor requires treatment of all subjects prior to each IP infusion to minimize the risk of a potential severe allergic reaction. It is strongly encouraged that pre-medication be administered according to the guidelines in [Table 6](#) including the administration of high dose steroids, H1 and H2 blockers; however, investigative sites may use institutional protocols established for anaphylaxis prevention should they be at least physiologically comparable to the guidelines below.

Final decisions regarding the medication(s), dose(s) administered, and route(s) of administration are to be determined by the Investigator taking into consideration the subject's medical history. For any pre-treatment medication administered, the FDA approved label should be reviewed for information on potential side effects and/or drug interactions and followed for detailed instructions on weight-based dosing.

Of note, for subjects routinely treated with beta blocker and ACEi, the doses of both should be held on the day of infusion, if clinically acceptable in the judgment of the site Investigator. Furthermore, it is recommended that the standing steroid doses should be held if the planned schedule is within 24 hours of the time of scheduled infusion of IP. This is because glucocorticoids will likely be administered as part of the pre-medications beginning 12 – 14 hours prior to infusion of IP.

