5.9 Prior and Concomitant Medications

Prescription, over-the-counter, and alternative medication use will be coded to drug class, preferred drug name, and generic/trade drug name using the World Health Organization Drug Global dictionary (WHODrug Global) version September 1, 2017. Medications that were stopped before the start of the IP administration procedure will be considered “pre-treatment.” All other medications will be considered “concomitant.” Medications that were started or ongoing at the time the IP administration procedure was started will be considered “baseline” (a subset of “concomitant”). Pre-treatment, baseline, and concomitant medications will be listed separately.

Frequencies and percentages of subjects reporting or receiving cardiac and steroid medications will be summarized by WHODrug Global Anatomic Therapeutic Chemical (ATC) Level 2 and Preferred Term. Pre-treatment and baseline cardiac and steroid medications will be summarized separately from concomitant cardiac and steroid medications.

At each level of subject summarization, subjects who reported one or more medication within that level are only counted once for that level.

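### SAP Addendum 3.2 sorts steroids into systemic and non-systemic use by indication instead of route, so an oral or IV steroid recorded for a non-DMD reason is tabled as non-systemic

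*SAP*

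**What the plan says.** SAP Addendum Section 3.2 summarises subjects who took steroids on or after Day 1 in two tables. The dividing rule is the reported indication. Steroids with reported "indications as DMD, DMD treatment, or SOC for DMD are considered for systemic use", while "steroid medications with other indications are considered for non-systemic use". On layout: "Both summaries will be presented by WHODrug Preferred Term". A listing is also planned: "All steroid medications on study, along with their reported indications, will be listed". Route is not named as a listed item.

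SAP v3.0 Section 5.9 has no such split. There, "cardiac and steroid medications will be summarized by WHODrug Global Anatomic Therapeutic Chemical (ATC) Level 2 and Preferred Term".

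The protocol bears on the rule in four places:

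- **Section 10.7:** "Capricor requires that subjects be treated prior to each IP infusion with medications to minimize the risk of potential severe allergic reaction".
- **Section 21.2 (Appendix II):** the strongly encouraged guideline is described as "including the administration of high dose steroids, H1 and H2 blockers". Final choice of drug, dose and route is left to the Investigator.
- **Section 10.6:** glucocorticoid premedication is expected to begin 12 to 14 hours before infusion, and the standing glucocorticoid is withheld around it.
- **Section 12.4:** for each medication, "generic name, indication, dose, frequency, route, and starting and stopping dates/times (if applicable) will be collected".

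**The concern.** Whether a steroid is used systemically depends on how it is given. The addendum uses the words systemic and non-systemic but decides between them by why the drug was given. The two agree for a boy's standing DMD steroid. They disagree for any oral or IV steroid given for another reason, and this protocol builds in such a use at every infusion.

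What is at stake is the accuracy of the descriptive steroid tables. Protocol Section 14.4.3 promises separate listings and summaries for glucocorticoids, and readers of the study report will take the table titles at face value. The non-systemic table would mix oral or IV premedication with topical and inhaled products. The same Preferred Term could appear as systemic in one table and non-systemic in the other solely because of the indication.

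**Working it through.** The plan states no figure on this point. The check applies the written rule to each kind of steroid use and compares the label with the route.

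| Steroid use | Indication as recorded | Label under Addendum 3.2 | Correct by route? |
|---|---|---|---|
| Standing glucocorticoid (inclusion criterion 8) | DMD | Systemic | Yes |
| Oral or IV premedication | Allergy prophylaxis | Non-systemic | No |
| Oral or IV premedication | DMD (if a site recorded it so) | Systemic | Yes |
| Oral or IV steroid for a reaction, if any | Reaction | Non-systemic | No |
| Oral or IV steroid for another condition | Non-DMD | Non-systemic | No |
| Topical or inhaled steroid | Non-DMD | Non-systemic | Yes |

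**Is the premedication systemic?** The readable text does not fix its route. Three features point that way: it is described as high dose, it is expected to start 12 to 14 hours ahead, and the standing systemic glucocorticoid is withheld when it is used. Withholding a systemic drug would make little sense if the substitute acted only locally. This is an inference.

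**Does it fall in the table window?** The window opens on Day 1. Premedication for the infusions at Months 3, 6 and 9 lies wholly inside it. For the first infusion, doses taken the evening before fall outside.

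**Size.** The tables report numbers and percentages of subjects, so the unit is the subject.

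- Ceiling: 20 randomized subjects, each with at least one qualifying premedication steroid, gives 20/20 = 100% of subjects with a systemic steroid in the non-systemic table.
- Floor: 0/20, if no steroid premedication was used or all of it was recorded under a DMD indication, and no other oral or IV steroid was given for a non-DMD reason.
- Subjects with any systemic use: inclusion criterion 8 requires a systemic glucocorticoid for at least 12 months before randomization, and Protocol Section 9.2 asks that the DMD regimen be kept. If those drugs carry a DMD indication, nearly all 20 are already in the systemic table. Moving premedication across changes Preferred Term rows but hardly the total.

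**Telling reaction treatment from premedication.** Suppose 10 subjects per arm (20 / 2, assuming exact balance), all premedicated with one Preferred Term. That row in the non-systemic table reads 10/10 versus 10/10. A steroid with the same Preferred Term given later for a reaction adds no subject to the row, in either arm. This is an illustration; the readable text does not describe steroids as treatment of reactions.

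**Could route have been used?** Yes. Protocol Section 12.4 collects indication and route for every medication, so no data limitation forces the choice of indication.

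**The case against.** The strongest reply is that this is a labelling fault in a post-hoc descriptive table, with a sensible purpose behind it: separating background DMD therapy from all other steroid use. The case has several parts.

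- **Nothing is dropped.** Premedication steroids appear in the second table, and the listing shows each steroid with its indication. With 20 subjects a reader can sort DMD therapy, premedication and other use by hand. This stands, though only in part: route is not a named item in the listing, so it may not settle which non-DMD uses were systemic.
- **SAP v3.0 Section 5.9 may still apply.** The addendum says that it details the steroid summaries further and does not say that it withdraws the unsplit ones. This is a fair reading. It would leave a correct unsplit table beside two with misleading titles.
- **Steroid premedication is encouraged, not mandated.** Sites may use comparable institutional protocols. This stands, and it is why 20 of 20 is a ceiling.
- **Retitling would suffice.** It would make the tables true, but it would not show systemic use by route.

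A reader might also infer that as many as 20 x 4 = 80 premedication courses are misplaced. The documents do not support that unit, because the tables count subjects and carry no courses, doses or durations.

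**Conclusion.** The rule is wrong as written. It labels steroid use by indication and calls the result systemic or non-systemic, so any oral or IV steroid with a non-DMD indication goes into the non-systemic table. Up to 20 of 20 subjects could be affected, assuming that steroid premedication was given orally or by IV on or after Day 1 and was not recorded under a DMD indication. The Preferred Term rows and the non-systemic table would be wrong; the count of subjects with any systemic use would barely move.

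Three stronger readings are tempting, and the documents do not carry them:

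- **That the tables materially understate systemic exposure.** All subjects enter on a systemic glucocorticoid, and a subject count would not measure cumulative exposure even if correctly labelled.
- **That the tables hide a difference between arms in treatment of reactions.** Such steroids, if any, would be misclassified and could not be told apart from premedication in the table. But no readable text describes that use (parts of Protocol Section 10 are redacted), and the listing would show the indication.
- **That efficacy results are confounded.** Premedication is required in both arms of a randomized, blinded trial, and no endpoint or model uses this split or a steroid variable.

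The defect is confined to the post-hoc steroid tables. It is worth correcting because the correction is cheap.

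**What to change.** In SAP Addendum Section 3.2, define systemic versus non-systemic by the recorded route: oral, IV and IM as systemic; topical, inhaled and ophthalmic as non-systemic. Within systemic use, show DMD maintenance separately from other indications, with infusion premedication and any treatment of reactions on their own lines. Add route to the steroid listing.

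At minimum, keep the present split and retitle the two tables as *DMD indication* and *other indication*, so that the titles describe what the rule does.

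The cost is one sentence in the addendum and two re-run descriptive tables, plus one added listing column, all from fields already collected. No endpoint, population, model or clinical rule changes.
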